Participant recruitment and study site: All women age 18-35 years old who present to a Planned Parenthood Association of Utah (PPAU) clinic requesting EC will receive a one-page handout offering (1) same-day method initiation with oral LNG + ENG implant or other hormonal method, (2) copper or LNG IUD alone, or (3) UPA with delayed initiation of hormonal contraception if BMI >30. Women initiating an ENG implant + oral LNG EC will be offered enrollment into a prospective observational survey study. All study procedures will occur at PPAU clinics. Standard clinical counseling at participating health centers includes differences in efficacy between oral LNG and UPA by BMI and in those between 3-5 days out from UPI. Women desiring the most effective oral method of EC will be offered ulipristal acetate.

Sample size: This is an observational trial to gain a point estimate for pregnancy rate following guideline-adherent, same-day method initiation with oral LNG + ENG implant compared to published pregnancy rates following oral LNG EC alone. [5] Our maximum sample goal is 300 women with 1-month pregnancy outcome data and the 1st 100 women will be followed for the secondary outcomes of 12-month continuation or reasons/timing of discontinuation. We will use the 2 PPAU clinics that dispense the greatest EC volume for this study (960 total EC visits in 2019) and plan to achieve our recruitment goal in 24 months. We are confident in our recruitment plan based on the 1,122 EC users receiving IUDs at these clinics who have enrolled in prospective clinical trials.

Our null hypotheses are:

- 1) ENG implant along with oral LNG EC will not have a pregnancy rate greater than published oral LNG EC (2.5%; 95%CI 1.3-4.6). [5]
- 2) Uptake of same-day ENG implants will be lower than same-day IUD uptake for EC.

Purpose and Objectives

Primary:

1. To determine a point estimate for the one-month pregnancy rate following guideline supported same-day initiation of an etonogestrel (ENG) implant plus oral levonorgestrel (LNG) emergency contraception (EC).
2. To determine the proportion of EC clients willing to initiate a same-day ENG implant with oral LNG EC compared to same-day initiation of intrauterine devices for EC.

Secondary:

- Describe the 6- and 12-month continuation rates of the ENG implant with same-day initiation at an EC encounter.
- Describe the timing and reasons for ENG implant discontinuation in the 12 months following same-day initiation at an EC encounter.

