Clinical hypotheses.

- Combined oral LNG EC administration with same-day ENG implant insertion will not increase pregnancy rate point estimate compared to oral EC alone.
- EC clients willing to initiate a same-day LARC method will preferentially chose the ENG implant over IUDs and
- Clients initiating a same-day ENG implant will continue the method at the same rate as users who initiate at other encounters.

Study Population

Age of Participants: Women age 18-35

Sample Size:

At Utah:

All Centers:

Inclusion Criteria:

Healthy women, age 18-35 years, fluent in English and/or Spanish

BMI < 30 kg/m²

No known contraindication to either the ENG contraceptive implant or oral LNG EC using the CDC Medical Eligibility Criteria for Contraceptive Use 2016

Negative urine pregnancy test

Willing to abstain from further UPI in the 7 days following insertion

Know the date of their last menstrual period

Have a regular menstrual cycle (24-35 days)

Be willing to comply with the study requirements, and

Desiring to avoid pregnancy for at least 12 months.

Their current preferred phone number must be functioning at the time of study entry and will be tested prior to enrollment. We will obtain preferred mode of communication (phone, text, email) and also a contact information for a secondary person.

Exclusion Criteria:

Current pregnancy or breastfeeding

Previous use of oral EC in the current cycle

Report of UPI beyond 5 days in current cycle

Vaginal bleeding of unknown etiology

Allergy to LNG or ENG

IUD or implant in-place

History of permanent contraception through sterilization or hysterectomy

Monogamous partner with a vasectomy, or

Depo-provera injection within past 15 weeks.

Design

Study Procedures

Recruitment/Participant Identification Process:

All clients who present to selected Planned Parenthood Association of Utah clinics for Emergency Contraception (EC) will receive a single-page explanation of EC options (attached in Documents section of study application) with ongoing contraception initiation: copper or LNG IUD alone, oral LNG EC + implant or other hormonal contraception, oral LNG EC alone, or oral UPA EC alone (with or without delayed initiation of hormonal contraception).

This explanation will end with an assessment of interest in a contraceptive visit, which allows us to gather information on women who refuse the counseling and opted to only access oral

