EC. This information will include: age, race/ethnicity, last menstrual period, and reason for declining counseling.

Women desiring additional information about the ENG implant will then be asked if she is interested in study participation, through a consent process managed by an IRB approved member of the study team.

Those with interest in other methods, including IUDs, will receive a contraceptive visit by PPAU clinical staff.

Informed Consent:

Description of location(s) where consent will be obtained:

Consent will be obtained in a private examination room at the clinic where the patient is receiving care.

Description of the consent process(es), including the timing of consent:

Due to the nature of this study, it may not be possible for patients to return at a later time to enroll in the study. Participants will have all questions answered prior to enrollment. The research staff are experienced in interviewing and working with this population. They will be certain to take the time needed to ensure that the patient understands the study and is consenting willingly. If the woman continues to have questions, she will be offered the opportunity to discuss the study in further detail with the PI or other medical providers with extensive experience with the clinical care of IUDs and emergency contraception.

Procedures:

Screening/enrollment Visit: Subjects interested in the ENG implant will be screened for eligibility and interest in the study. Each subject will have the study explained and, if she desires to participate, she will sign the informed consent prior to any study procedures. The screening/enrollment visit will include: review of medical, surgical and social history, medications, contraceptive use, height and weight to calculate BMI <30, and a urine pregnancy test. We will collect detailed information on menstrual cycle history, last menstrual period, cycle length over the preceding six months, and time of unprotected intercourse. This will enable us to calculate the timing of UPI relative to position in the menstrual cycle should any pregnancies occur. Finally, we will insert the ENG implant with co-administration of oral LNG EC (1.5mg po X1). Participants will be given a home pregnancy test with instructions on use at 1 month. They will also have a clinic appointment made for 1 month, in case of need for in-person urine pregnancy testing or follow-up from a positive home pregnancy test.

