Women who choose an IUD: Women who choose an IUD and agree to participate in this study will be asked to sign the consent document. They will then be asked to complete a questionnaire about prior sexual activity, use of contraception, pregnancies and sexually transmitted infections. Completion of this questionnaire will be the only study procedure asked of this subgroup of participants. There will be no follow-up procedures.

One-month follow-up (Phone or in-person): Four weeks after enrollment, the research staff will contact the participant per their contact preference (text, phone, etc.) and send a link to a

RedCAP survey to record the results of their home pregnancy test, assess satisfaction with the implant and record any adverse events that have occurred. If the participant is unable to complete the home pregnancy test and record results, a clinic visit will be scheduled for a urine pregnancy test. If a patient has a positive pregnancy test, she will receive an ultrasound, a blood test for b-HCG, standard pregnancy options counseling and removal of the implant will be recommended if she opts to continue the pregnancy. Participants will receive \$40 for this follow-up.

Three-month follow-up (Online link or Phone):* Three months after enrollment, participants will receive a link to a RedCAP survey to assess satisfaction with the implant and adverse events. If the participant has discontinued the method, we will collect the date of discontinuation, reason(s) and current contraceptive method. If the survey is not completed within 7 days, the research staff will complete up to 3 attempts to contact the participant by each contact method for survey administration. No compensation for this call.

Six-month follow-up (Online link or Phone):* Six months after enrollment, participants will receive a link to a RedCAP survey to assess satisfaction with the implant and adverse events. If the participant has discontinued the method, we will collect the date of discontinuation, reason(s) and current contraceptive method. If the survey is not completed within 7 days, the research staff will complete up to 3 attempts to contact the participant by each contact method for survey administration. Participants will receive \$20 for this follow-up.

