ENG implants will be supplied via Merck. Oral LNG EC is provided at no cost from PPAU and the study team will provide the other LARC (long acting reversible contraception) methods, the copper and LNG IUD, at no cost to avoid bias in LARC preference. All devices and the oral LNG EC are FDA approved and will be maintained in their usual packaging.

The investigator will be responsible for the destruction of the supplies at the study center pursuant to the ICH/GCP Guidelines, local regulations and the investigator's institutional policies. Clinical supplies will be received by a designated person at the study site, handled and stored safely and properly, and kept in a secured location to which only the investigator and designated assistants have access. The investigator will be responsible for keeping accurate records of the clinical supplies, the amount dispensed to and returned by the patients, and the disposition at the end of the study.

Procedures performed for research purposes only:

Study procedures involve women who present to Planned Parenthood for emergency contraception but who are also looking for long-acting reversible contraception at the same time as emergency contraception (EC).

Study procedures include:

Enrollment survey and choice of either a Nexplanon implant plus Plan B for emergency contraception or an IUD (either hormonal or copper) for EC and continued contraception.

Individuals who chose the Nexplanon implant plus Plan B will then be asked to provide pregnancy information at one month plus satisfaction surveys at 3, 6, 9, and 12 months.

Statistical Methods, Data Analysis and Interpretation

The investigator and study team will be responsible for analyzing the study data. The official clinical database in RedCAP will not be analyzed until medical/scientific review has been completed, protocol violations have been identified (if appropriate), and data has been declared complete.

Variables/Time Points of Interest

The primary outcomes are 1) pregnancy rate calculated as the proportion of women with a positive pregnancy test at 1 month following the enrollment and 2) proportion of EC clients willing to initiate a same-day contraceptive implant. Secondary outcomes will be implant continuation at 6 and 12 months and timing and reasons for discontinuation.

Statistical Methods

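### As described in the recruitment section, the study offer, screen and payments reach implant-interested women before their choice is recorded and IUD choosers only afterwards or not at all, so the co-primary implant-versus-IUD comparison is at risk of bias of unknown direction

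*Combined protocol and SAP*

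**What the plan says.** Purpose and Objectives gives the second primary objective as "To determine the proportion of EC clients willing to initiate a same-day ENG implant with oral LNG EC compared to same-day initiation of intrauterine devices". Variables/Time Points of Interest shortens this to "proportion of EC clients willing to initiate a same-day contraceptive implant", and Clinical hypotheses adds a direction: "EC clients willing to initiate a same-day LARC method will preferentially chose the ENG implant over IUDs". Null hypothesis 2, under Sample size, is framed in terms of uptake.

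Under Recruitment/Participant Identification Process every EC client receives a one-page option sheet, and "This explanation will end with an assessment of interest in a contraceptive visit". After that the routes divide. For the implant, "Women desiring additional information about the ENG implant will then be asked if she is interested in study participation". For the rest, "Those with interest in other methods, including IUDs, will receive a contraceptive visit by PPAU clinical staff".

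The paragraph on women who choose an IUD says that they too may consent to the study and complete a questionnaire, and that "Completion of this questionnaire will be the only study procedure asked of this subgroup of participants".

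Electronic Health Record Data Extraction takes method choices from the records of all EC encounters in the study period. Statistical Methods reports them descriptively over all EC clients. The one stated control on preference concerns cost: the study supplies IUDs "at no cost to avoid bias in LARC preference".

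**The concern.** A preference comparison is sound when both options are met on equal terms up to the moment the choice is recorded. The protocol accepts this for device cost. It does not extend it to the study offer, the eligibility screen or the follow-up payments. As the recruitment section describes matters, these fall on women asking about the implant before an implant is placed. Women choosing an IUD meet a lighter study offer only after choosing.

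The estimate at stake is a co-primary one. If study conduct shifts some choices, the reported implant and IUD proportions partly describe the study and not what EC clients want. Without a preference recorded before the study is mentioned, later analysis cannot separate the two.

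**Working it through.** The documents give no sample size, power, expected proportion or test for objective 2, so there is no planned figure to reproduce. The check is mainly a comparison of sections.

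**1. What is recorded before the study is mentioned.** The option sheet is described as ending with interest in a contraceptive visit. The further items listed (age, race/ethnicity, last menstrual period, reason for declining) concern women who refuse counseling. No implant-versus-IUD item is described.

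**2. The two routes, from the sections on recruitment, the screening/enrollment visit, women who choose an IUD, and the follow-up contacts.**

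| Step | Implant | IUD |
|---|---|---|
| Trigger for study offer | Wanting information | Having chosen the device |
| Seen by | Study team for consent | Clinic staff for the contraceptive visit |
| Screen before the device | Yes: for example cycle of 24-35 days, known last menstrual period, BMI under 30, no oral EC earlier in the cycle, working phone | None described |
| Study burden | 1-month pregnancy test; surveys at 3 to 12 months for the first 100 who agree | One questionnaire |
| Payment described | $40 at 1 month; $20 at 6 and $20 at 12 months | None |

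**3. When the implant offer is made.** The recruitment section places it at interest in information, and the screening/enrollment visit puts consent and screening before insertion. Participant recruitment and study site places it with women already initiating the implant. Under the second sequence the choice comes before the offer; under the first it does not. The text does not settle which one staff would follow.

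**4. What the records recover.** Extraction covers all EC encounters, so women who do not enroll are still counted. It records the method at EC provision (or at the later visit after ulipristal). In the recruitment section's sequence that is after the offer and screen. A complete denominator does not restore a choice altered earlier.

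**5. Size of the payment.** The maximum is 40 + 20 + 20 = $80, but the last $40 goes only to the first 100 who agree to longer follow-up. With 300 women in the primary analysis, at least 300 − 100 = 200 would have $40 described.

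**6. Direction (illustration only; every input is an assumption).** Suppose true preference among same-day LARC choosers is 50:50. Let e be the fraction of implant-preferring women lost at the screen or offer, s the fraction of those who take an IUD instead, and q the fraction of IUD-preferring women drawn to the implant.

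Implant share = [0.5(1 − e) + 0.5q] / [0.5(1 − e) + 0.5q + 0.5(1 − q) + 0.5es]

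- Loss only, e = 10% to 40%, no switching (s = 0): 0.45/0.95 = 47.4% to 0.30/0.80 = 37.5%.
- Loss only, e = 10% to 40%, all switching (s = 1): 45.0% to 30.0%.
- Payment only, q = 5% to 20%: 52.5% to 60.0%.
- Both, e = 20%, q = 10%, s = 0: 0.45/0.90 = 50.0%.

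The observed share can move either way or not at all. These values show that the sign is open; they do not estimate a bias in this trial.

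**The case against.** The strongest reply has five parts.

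- **All EC encounters are counted.** This stands as far as it goes: enrollment does not decide who enters the comparison. It does not answer an influence on the choice itself.
- **IUD choosers are also invited into the study.** This is correct. A reader might infer that they never meet a study offer, and the protocol says otherwise. The remaining difference is timing, burden and described payment.
- **Payment is not shown to draw anyone across.** Women approached about the implant have already asked about it, and nothing says that IUD-interested women hear of the payments before choosing. This narrows the mechanism mainly to undecided women asking about the implant. It does not remove it.
- **The screen may not reduce uptake.** A reader might infer that a woman who fails the criteria leaves without an implant. The protocol does not say so. It is silent on whether she can have a same-day implant outside the study, and on its cost.
- **The option sheet and consent pages are not in the text reviewed.** The sheet may already ask about method, and payment to IUD participants may be described elsewhere. This stands, and the fix is conditional on it.

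A preference ticked before counseling is also not the same as uptake. Null hypothesis 2 concerns uptake, and the background notes that women seeking EC may not have thought about LARC beforehand. That is a good reason not to replace uptake as the outcome.

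**Conclusion.** The concern holds as a risk of bias of unknown direction and size in the co-primary comparison. It rests on three assumptions: staff follow the recruitment section's sequence, payments are explained with the study offer, and the option sheet has no method item. If the study were raised only with women already initiating the implant, most of the concern would fall away. The conflict between the two sections is therefore the main defect.

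A reader might infer more: that the result is biased toward the implant, that the preference hypothesis cannot be answered, or that a falsely significant preference will follow. The documents support none of these. Payment and screening act in opposite directions, no input fixes the net effect, and Statistical Methods plans only descriptive reporting of method choice, so the issue is a possibly distorted estimate and not a test error. Nor does $80 apply to every implant participant. The point still deserves action before enrollment, because a preference not recorded before the offer cannot be obtained afterwards.

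**What to change.** 1. Reconcile Participant recruitment and study site with Recruitment/Participant Identification Process and the screening/enrollment visit, so that the study and its payments are raised only after the woman's method choice is recorded. Consent would still precede any study procedure.
2. Unless the option sheet already has one, add an item asking which method she would like to start today (implant with oral LNG, copper IUD, LNG IUD, other, none), completed before the study is mentioned.
3. Keep uptake from the health records as the objective 2 outcome, and report the pre-offer preference beside it.
4. State what the documents now leave open: whether women who fail the screen or decline the study can receive a same-day implant, and on what cost terms. That decides whether the screen can affect uptake at all.

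The cost is one form item and wording changes. The small downside is that preference stated before counseling may differ from uptake, which is why both are reported.

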We will calculate the one-month pregnancy rate and confidence intervals will be constructed using effective sample size adjustments for the small sample size. We will report descriptive data on the methods chosen from all EC clients during the study timeframe, as well as the responses from the informational assessment on those not interested in an ongoing contraceptive method the same day. Kaplan-Meier estimates will be constructed to estimate the proportion of patients who continue with their implant for 1 year (continuation proportion) and to estimate the proportion that have an unintended pregnancy by 1 year.

Power/Sample Size:

This study seeks to obtain point estimates to evaluate guideline-adherent care and for future study evaluations/comparisons. Guidelines allow for same-day initiation of the ENG implant with oral LNG EC, with the unstudied assumption that pregnancy rates will be equivalent. With this assumption, we anticipate a 2.5% pregnancy rate (95% CI= 1.3-4.6) based on the Glasier article estimate of pregnancy rate in the upper BMI range (25-29.9) with use of oral LNG EC alone. [5] In our recent IUD EC trial the median BMI was 25. The potential exists for higher pregnancy rates in BMI >30, thus we will exclude this population and recommend oral UPA as the preferred EC if an IUD is not desired. Because additional episodes of UPI in the same menstrual cycle following EC increase risk of pregnancy, inclusion criteria include a recommendation to avoid UPI for 7 days after enrollment.

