We plan for a sample size of a maximum of 300 participants for the primary outcome. This is based on the below table demonstrating the 95% CI and margin of error for sample size and upper limit CI of 5.0. We will analyze our pregnancy rate starting at 100 participants with 1-month pregnancy outcome data and with every subsequent 50 participants. We establish stopping rules demonstrating efficacy. For example, we will stop trial enrollment if the 1-month pregnancy point estimate is <2% AND the top end of the 95% CI is <5%. This would occur if 2 (or fewer) pregnancies occurred with 1-month pregnancy outcomes for 200 participants. This would yield a point estimate of 1% and a 95% CI (0-3.8%). There is not a perceived risk of having a 1-month pregnancy rate greater than what is known for oral LNG for EC. However, we have developed a stopping point if there is an unknown interaction or effect of combined use of oral LNG and ENG implant initiation. Once we have outcome data on 100 participants, we will cease trial enrollment if the point estimate for the 1-month pregnancy rate exceeds the known upper bound of the 95% CI for women with in the upper BMI range (25-29.9) using oral LNG EC (4.6, from Glasier estimate above).

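### The implant-versus-IUD uptake comparison is a primary objective with its own null hypothesis, but the plan gives it no comparator in the outcome and no measure of uncertainty

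*Combined protocol and SAP*

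**What the plan says.** All references are to the combined protocol and SAP.

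- **Purpose and Objectives, second primary objective:** "To determine the proportion of EC clients willing to initiate a same-day ENG implant with oral LNG EC compared to same-day initiation of intrauterine devices". This is worded as a comparison.
- **Sample size, null hypothesis 2:** "Uptake of same-day ENG implants will be lower than same-day IUD uptake for EC". This is comparative and directional.
- **Clinical hypotheses:** "EC clients willing to initiate a same-day LARC method will preferentially chose the ENG implant over IUDs". This takes the opposite direction to null 2, and its denominator is clients willing to start a LARC method rather than all EC clients.
- **Variables/Time Points of Interest, primary outcome 2:** "proportion of EC clients willing to initiate a same-day contraceptive implant". The IUD comparator is absent.
- **Statistical Methods, uptake:** "We will report descriptive data on the methods chosen from all EC clients during the study timeframe".
- **Statistical Methods, pregnancy:** "We will calculate the one-month pregnancy rate and confidence intervals will be constructed using effective sample size adjustments for the small sample size". The section mentions intervals nowhere else.
- **Power/Sample Size:** the maximum of 300, the interim looks and the stopping rules all concern the one-month pregnancy rate. Nothing is said about precision for uptake.
- **Electronic Health Record Data Extraction:** the records are to be searched for EC encounters, and the method chosen is recorded for each.

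**The concern.** Objective, hypothesis, outcome and analysis do not line up for one of the two primary questions. The objective and the null ask whether implant uptake falls below IUD uptake. The outcome measures one arm of that comparison, and the analysis describes counts without saying how precisely they are known.

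The study could therefore end with a table of methods chosen and a stated null hypothesis, with nothing planned to connect the two. A modest excess of either method could reflect preference or chance, and the report would not show which. The denominator is also open: the objective speaks of EC clients, the clinical hypothesis of LARC choosers, and the data source counts encounters.

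**Working it through.** **1. Stated figures.** The plan gives no sample size, precision, significance level or interval for null 2, so there is none to reproduce. The only same-day uptake figure with a denominator is the historical one in the background: 33 copper IUDs + 3 LNG IUDs + 2 implants = 38, and 38/328 = 11.6%, which rounds to the stated 12%.

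**2. Inputs for an illustration.**
- Implants: 300, the maximum enrolment in Power/Sample Size. This is the number of study participants. The number of EC clients starting an implant in the health records may differ.
- IUDs: not given. I assume 280 and show a range.
- EC visits: 960 in 2019 (Sample size) × 2 years of recruitment = 1,920, assuming constant volume. These are visits, not clients.

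**3. Implant share among same-day LARC starts** (the denominator of the clinical hypothesis). Share = implants/(implants + IUDs), with an exact (Clopper-Pearson) 95% interval.

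| Implants | IUDs (assumed) | Implant share | Exact 95% CI |
|---|---|---|---|
| 300 | 300 | 50.0% | 45.9 to 54.1% |
| 300 | 280 | 51.7% | 47.6 to 55.9% |
| 300 | 260 | 53.6% | 49.3 to 57.8% |
| 300 | 240 | 55.6% | 51.3 to 59.8% |
| 100 | 90 | 52.6% | 45.3 to 59.9% |
| 100 | 80 | 55.6% | 48.0 to 63.0% |

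The rows with 100 implants stand for enrolment ending at the first planned look. With 300 v 280 the two-sided exact binomial p-value against 50% is 0.43. The same share of 55.6% excludes 50% with 300 implants but not with 100, so the percentages alone do not settle the matter.

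**4. Difference per EC client** (the denominator of the objective). Each client starts either an implant or an IUD, so the two counts are exclusive categories of one sample. With p1 and p2 the two proportions among N clients, the variance of p1 − p2 is [p1 + p2 − (p1 − p2)²]/N.
- p1 = 300/1,920 = 15.63%; p2 = 280/1,920 = 14.58%; difference 1.04 points.
- SE = √[(0.30208 − 0.00011)/1,920] = 1.25 points.
- 95% CI = 1.04 ± 1.96 × 1.25 = −1.4 to 3.5 points.
- If N were 960, with the same counts: difference 2.08 points, SE 2.51, 95% CI −2.8 to 7.0.

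**5. How often chance alone gives an excess.** With 600 same-day LARC starts (assumed), the binomial chance of more implants than IUDs is 48% if preference is truly equal, and 15% if the true implant share is 48%.

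**The case against.** The strongest reply is that Power/Sample Size describes a study that seeks point estimates for later comparisons. Uptake is called descriptive, the sample size rests on pregnancy, and the pregnancy outcome has no formal hypothesis test either. An interval could be added at reporting from data already extracted.

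Much of that stands. A formal test is not required, and nothing in data collection is at risk. It does not explain why one primary outcome gets a confidence interval and the other does not, nor why a null hypothesis is stated with no means of judging it.

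Three stronger readings are tempting, but the documents do not support them:

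- **That any raw excess of implants will be taken as rejecting null 2.** The plan contains no decision rule for null 2, raw or otherwise. Raw percentages are merely all that it provides.
- **That the plan would use a test with the wrong standard error.** No section proposes comparing the two uptakes as independent samples. The shared client pool matters only for choosing the interval to add.
- **That a particular number of IUDs marks the boundary for rejecting null 2.** Any such limit depends on sidedness and significance level, and the documents set neither.

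**Conclusion.** The point holds as a mismatch between a comparative primary objective with a directional null and an outcome and analysis that provide neither comparator nor uncertainty. With 300 implants and IUD counts near that number, the exact interval for the implant share extends about 4 percentage points each side, so a lead such as 300 v 280 is inconclusive. With 100 implants it extends about 7 points.

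These sizes rest on assumed IUD counts, on taking the enrolment maximum as the implant count and, for the per-client difference, on 2019 visit volume holding for 24 months with one visit per client. If the split were as lopsided as the historical 36 IUDs to 2 implants, the direction would be clear without an interval. The gap matters when the two uptakes are close. It does not touch the pregnancy outcome, its sample size or its stopping rules.

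I class it as a free improvement.

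**What to change.** 1. **Variables/Time Points of Interest:** add same-day IUD initiation as the comparator in primary outcome 2, to match the objective's "compared to same-day initiation of intrauterine devices for EC".
2. **Statistical Methods:** report the implant share among clients starting a same-day LARC method with an exact binomial 95% CI, judged against 50%.
3. **Statistical Methods:** report the implant-minus-IUD difference per EC client with a 95% CI based on the multinomial variance above.
4. **Denominator:** state which of the two is primary.
5. **Unit:** count one encounter per client, since the records are extracted by encounter and repeat visits by one client are not independent.
6. **Null 2:** either state whether its assessment is one-sided or two-sided, or withdraw it and report the intervals only.

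The cost is some plan wording and a few lines of analysis on data that the health-record extraction already provides. No participant procedure changes. The one downside is that a small raw difference may have to be reported as inconclusive.
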